9.1 Study Design

This is a prospective, observational, exposure cohort study (Registry) of fetal, infant, and childhood outcomes in women who have been diagnosed with ASCVD, or hypercholesterolemia associated with FH, and who have been exposed to evolocumab during pregnancy, compared to fetal, infant, and childhood outcomes in women with these same diseases/conditions who have not been exposed to evolocumab during pregnancy (disease-matched comparison group), and fetal, infant, and childhood outcomes in women not diagnosed with these same conditions (non-disease-matched comparison group) who have not been exposed to evolocumab during pregnancy.

The Registry cohort study will be conducted by investigators at the University of California Research Center for the Organization of Teratology Information Specialists (OTIS). OTIS is a network of university and health department based telephone information centers serving pregnant women and health care providers throughout North America ([Leen-Mitchell et al, 2000](#)). These services receive spontaneous telephone inquiries from women who are pregnant or considering pregnancy as well as from healthcare providers about the safety or risk associated with environmental exposures in pregnancy, including medications. Trained Teratogen Information Specialists at each site provide appropriate risk assessment and referral for all patient and health care provider callers free of charge. These services also provide a basis for collaborative research such as this Registry. Thus, individual Teratogen Information Services located throughout the US and Canada will serve as a source of referrals not only for evolocumab-exposed pregnancies, but also for similarly ascertained pregnant women frequency-matched to the evolocumab-exposed pregnancies by disease indication who have not used evolocumab, and similarly ascertained pregnant women not diagnosed with ASCVD or hypercholesterolemia associated with FH who have not used evolocumab, nor any known human teratogen to serve as a general population comparator. In addition to the above-specified means of identification, Amgen will attempt to facilitate identification of potentially eligible women via its network of providers who are most likely to treat women of child-bearing age with an indicated condition (eg, women with FH).

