9.2.3 Subject Eligibility

9.2.3.1 Inclusion Criteria

(1) Specific Evolocumab-Exposed Cohort

- Qualified subjects will be currently pregnant women (maternal report validated by medical records) diagnosed with ASCVD, or hypercholesterolemia associated with FH who have been exposed to evolocumab for any number of days, at any dose, and at any time from the first day of the LMP up to and including the end of pregnancy. If the date of the LMP is unclear, or if a first-trimester ultrasound has been done and the estimated date of conception is more than 1 week discrepant from the menstrual period calculation, the first-trimester ultrasound-derived date will be used to calculate a date for LMP and conception.
- Qualified subjects will agree to the conditions and requirements of the study including the interview schedule, release of medical records, the physical examination of live born infants, and 5 years of follow-up.

(2) Comparison Group I

- Qualified subjects will be currently pregnant women (maternal report validated by medical records) diagnosed with ASCVD, or hypercholesterolemia associated with FH but who were not exposed to evolocumab during pregnancy or any time within 90 days prior to the first day of the LMP.
- Qualified subjects will agree to the conditions and requirements of the study including the interview schedule, release of medical records, the physical examination of live born infants, and 5 years of follow-up.

(3) Comparison Group II

- Qualified subjects will be currently pregnant women not diagnosed with ASCVD, or hypercholesterolemia associated with FH, who have not been exposed to evolocumab during pregnancy or any time within 90 days prior to the first day of the LMP, and who have no exposure to any known human teratogens as determined by the OTIS Research Center.
- Qualified subjects will agree to the conditions and requirements of the study including the interview schedule, release of medical records, the physical examination of live born infants, and 5 years of follow-up.

(4) General Evolocumab-Exposed Case Series

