9.2.3.2 Exclusion Criteria

(1) Specific Evolocumab-Exposed Cohort

- Women who first contact the Registry after prenatal diagnosis of a major structural **birth** defect
- Women who were exposed to a different PCSK9 inhibitor during their current pregnancy or at any time within 5 half-lives prior to the first day of the LMP
- Women who have enrolled in this Registry with a previous pregnancy

(2) Comparison Group I

- Women who first contact the Registry after prenatal diagnosis of a major structural **birth** defect
- Women who have enrolled in this Registry with a previous pregnancy
- Women who were exposed to **any** PCSK9 inhibitor during their current pregnancy or at any time within 5 half-lives prior to the first day of the LMP

(3) Comparison Group II

- Women who first contact the Registry after prenatal diagnosis of a major structural **birth** defect
- Women who were exposed to any PCSK9 inhibitor during their current pregnancy or at any time within 5 half-lives prior to the first day of the LMP
- Women who have enrolled in this Registry with a previous pregnancy

(4) General Evolocumab-Exposed Case Series

- None

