9.3.3.2 Exposure Interview Form

(At scheduled time points during pregnancy and post-delivery) Variables collected include current medication use (prescription and OTC); environmental and occupational exposures; alcohol, tobacco, caffeine, illicit drug use; current pregnancy complications; contact information of health care providers (see [Appendix A](#), 02.C. Exposure Interview Form).

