9.7.2.5 Analysis of the Primary, Secondary, and Exploratory Endpoint(s)

9.7.2.5.1 Primary Analysis

Comparison of the primary outcome between the Specific Evolocumab-Exposed cohort and Comparison Group I will serve as the primary analysis.

Comparison of the prevalence of major structural **birth** defects between the Specific Evolocumab-Exposed cohort and Comparison Group I will be among all live births and, separately, among all pregnancies excluding those lost to follow-up.

Outcomes that are adjudicated as not associated with drug exposure will be excluded from the primary analysis, but included in a sensitivity analysis ([Section 9.7.2.6](#)).

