9.7.2.5.2 Secondary Analysis

The following will comprise the secondary analyses:

1. Comparison of all secondary outcomes between the Specific Evolocumab-Exposed cohort and Comparison Group I
2. Comparison of the primary and all secondary outcomes between the Specific Evolocumab-Exposed cohort and Comparison Group II

The comparison of the prevalence of the total proportion of major structural **birth** defects between the Specific Evolocumab-Exposed cohort and Comparison Group II will be among all live births and, separately, among all pregnancies excluding those lost to follow-up. The comparison of the prevalence of ≥ 3 minor malformations between the Specific Evolocumab-Exposed cohort and each of the 2 comparison groups will be among children who receive the dysmorphological examination. The comparison of IgG-tetanus antibody status (test negative or indeterminate vs test positive) by group (Exposed, Comparison Group I, Comparison Group II) among those in the biological sample sub-study.

In each cohort we will separately calculate the proportion of all pregnancies ending in live birth, spontaneous abortion, stillbirth, elective termination, and lost to follow-up; crude comparisons will be made between cohorts.

The evaluation for a pattern of minor structural **birth** defects will be conducted using the following steps:

1. A comparison among groups of the proportion of infants with any 3 or more minor structural **birth** defects will be made without regard to pattern
2. Among infants with 3 or more minor **structural birth** defects, the Evolocumab-Exposed group will be examined for evidence of a specific pattern of 3 or more defects in any 2 or more children. If such a pattern is identified, Comparison Groups I and II will be evaluated for any evidence of the same pattern.

In each cohort among all live born infants we will separately calculate the proportion of premature delivery, small for gestational age on weight, length or head circumference, and rates of serious infections, hospitalizations, adverse vaccine reactions, and adverse neurodevelopmental outcomes; crude comparisons will be made between cohorts.

Mean birth weight, length and head circumference for full-term live born infants will be compared between cohorts. Postnatal growth parameters will be compared using the proportion of infants ≤ 10 th centile for sex and age with respect to weight, height, or head circumference.

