9.9 Limitations of the Research Methods

The primary limitation of a cohort study utilizing volunteer subjects is selection bias. The use of comparably selected comparison women will address this concern to some extent, and support internal validity of the results. The use of a volunteer sample may not be representative of the entire population of evolocumab-exposed pregnancies. However, use of a disease-matched comparison group will allow for internal validity of comparisons.

It is likely that women prescribed evolocumab will be more severely diseased than the women in Comparison Group I (disease-matched control group), leading to confounding by indication. In addition, subjects in the Evolocumab-Exposed group are more likely to be exposed to additional medications to lower their LDL-C levels (including multiple medications and higher doses). Confounding by indication may also vary over time with increased awareness and access to the drug. In order to attempt to mitigate biases associated with confounding by indication, the Registry proposes to collect careful measurements of comorbidities including maternal cholesterol levels and comorbidities including cardiovascular disease history that are likely to differ across cohorts. Additionally, methods such as propensity scores may be utilized in attempts to balance covariates between comparison groups. Nonetheless, unmeasured confounding remains a limitation of the observational study design and should be recognized when interpreting results.

It is unknown to what extent women who agree to enroll in the cohort study may represent particularly high or low risk pregnancies. However, the study results will be strictly applicable to women fitting the profile of the sample of women who enroll.

The overall sample size is expected to be modest and limits the statistical power to detect differences on the primary and secondary endpoints. However, given the necessity and value of the study questions, we will capitalize on getting the most complete data possible regardless of the expected low frequency of pregnancy exposure to evolocumab.

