8.1.2 Endpoints? (e.g. clinical records, laboratory markers or values, claims data, self-report, patient interview including scales and questionnaires, vital statistics, etc.)				9.3.2
8.1.3 Covariates?				9.3.3
8.2 Does the protocol describe the information available from the data source(s) on:				
8.2.1 Exposure? (e.g. date of dispensing, drug quantity, dose, number of days of supply prescription, daily dosage, prescriber)				9.3.1
8.2.2 Endpoints? (e.g. date of occurrence, multiple event, severity measures related to event)				9.3.2
8.2.3 Covariates? (e.g. age, sex, clinical and drug use history, co-morbidity, co-medications, life style, etc.)				9.3.3

Section 8: Data sources	Yes	No	N/A	Page Number(s)
8.3 Is a coding system described for:				
8.3.1 Diseases? (e.g. International Classification of Diseases (ICD)-10)				9.3.1
8.3.2 Endpoints? (e.g. Medical Dictionary for Regulatory Activities (MedDRA) for adverse events)				9.3.2
8.3.3 Exposure? (e.g. WHO Drug Dictionary, Anatomical Therapeutic Chemical (ATC) Classification System)				
8.4 Is the linkage method between data sources described? (e.g. based on a unique identifier or other)				

Comments:

Exposure coding is not applicable because Repatha (evolocumab) is the only exposure. Covariates and concomitant medication use other than Repatha will be reported descriptively; it is not anticipated that analyses by covariate subgroups will be performed. No linkage will be performed.

Section 9: Study size and power	Yes	No	N/A	Page Number(s)
9.1 Is sample size and/or statistical power calculated?				9.5

Comments:

Section 10: Analysis plan	Yes	No	N/A	Page Number(s)

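### The known-teratogen exclusion applies to Comparison Group II only, so the crude evolocumab versus Group II comparison is biased upward if any exposed women took a listed teratogen, and the protocol specifies no matching restriction or adjustment.

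*Protocol*

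**What the plan says.** Section 9.2.3.1 requires Comparison Group II to consist of women "who have no exposure to any known human teratogens as determined by the OTIS Research Center". Section 9.1 gives the reason: these women have used neither evolocumab "nor any known human teratogen to serve as a general population comparator".

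The inclusion and exclusion lists for the Specific Evolocumab-Exposed cohort and for Comparison Group I contain no teratogen criterion. The only drug exposure that excludes a woman from the exposed cohort is in Section 9.2.3.2: "Women who were exposed to a different PCSK9 inhibitor during their current pregnancy or at any time within 5 half-lives" before the last menstrual period.

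On analysis, Section 9.7.2.5.1 states: "Comparison of the primary outcome between the Specific Evolocumab-Exposed cohort and Comparison Group I will serve as the primary analysis". Section 9.7.2.5.2 lists as secondary: "Comparison of the primary and all secondary outcomes between the Specific Evolocumab-Exposed cohort and Comparison Group II". It calls for crude comparisons of pregnancy outcomes and of several infant outcomes. It then adds, in general terms, adjusted estimates by Cox, logistic or linear regression, with propensity scores to be considered. Section 9.7.2.6.1 limits subgroup analyses to timing and length of evolocumab exposure. Section 9.7.2.6.3 marks sensitivity analysis for residual confounding and bias as not applicable.

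On co-medication, Section 9.3.3.2 says: "Variables collected include current medication use (prescription and OTC"). Section 9.9 acknowledges that "subjects in the Evolocumab-Exposed group are more likely to be exposed to additional medications to lower their LDL-C levels". The comment under Section 8 of the Appendix B checklist says: "Covariates and concomitant medication use other than Repatha will be reported descriptively".

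**The concern.** A woman taking evolocumab together with a known teratogen can enter the exposed cohort. A woman taking the same teratogen without evolocumab is barred from Group II. One source of risk for birth defects and pregnancy loss is therefore removed from one side of the comparison by rule and left on the other. Any resulting bias in the crude Group II contrast runs against evolocumab.

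The protocol does not say that the exposed cohort will be restricted in the same way for this comparison, nor that teratogen co-exposure will be an adjustment variable. Section 9.9 does not list the asymmetry among the limitations. At stake is the reading of a raised relative risk against Group II in a cohort analysis that is to be tested at the 0.05 level: part or all of it could come from co-medication.

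**Working it through.** **1. Eligibility side by side (Sections 9.2.3.1 and 9.2.3.2).**

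| Group | Known teratogen allowed? | Role |
|---|---|---|
| Exposed cohort | Yes, no criterion | Exposed arm |
| Comparison Group I | Yes, no criterion | Primary comparator |
| Comparison Group II | No | Secondary comparator |

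The rule is one-sided against Group II and even-handed against Group I.

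**2. Size of the bias in the crude Group II contrast.** Let b be the outcome risk without a teratogen, p the share of the exposed cohort that took a listed teratogen, and r the relative risk that the teratogen carries. With no evolocumab effect:

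- risk in the exposed cohort = b[(1 − p) + pr] = b[1 + p(r − 1)]
- risk in Group II = b
- crude RR = 1 + p(r − 1)

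The documents give neither p nor r, so both are assumptions:

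| p | r = 2 | r = 3 |
|---|---|---|
| 5% | 1.05 | 1.10 |
| 10% | 1.10 | 1.20 |
| 20% | 1.20 | 1.40 |

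**3. Chance of a false excess.** Inputs from Section 9.5 and Table 3 are 71 exposed, 142 in Group II, a 4% baseline rate and a two-sided 5% test. Exact enumeration of Fisher's test gives these probabilities of a significant excess in the exposed group with no evolocumab effect:

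- no bias: 2.3%
- p = 10%, r = 2: 3.2%
- p = 20%, r = 2: 4.2%
- p = 20%, r = 3: 6.9%

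**4. Can adjustment repair it?** Three of the four evolocumab-by-teratogen cells are occupied: Group II without teratogen, exposed without, and exposed with. A model with an intercept, an evolocumab term and a teratogen term has rank 3 of 3, so the evolocumab effect is estimable. Fitted to expected counts with p = 20%, r = 2 (crude RR 1.20), it returns 1.00.

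Adding an evolocumab-by-teratogen interaction gives rank 3 of 4, so the effect among teratogen users is not estimable. Propensity methods have no Group II counterpart for those women.

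Adjustment also costs precision. The standard error of the log RR rises from 0.67 to 0.77 at p = 20%, r = 2. That is also the precision after restriction: with 71 × 0.8 = 56.8 teratogen-free exposed women, √[0.96/(56.8 × 0.04) + 0.96/(142 × 0.04)] = 0.77.

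**5. Power cost of restricting the exposed cohort.** At RR 3.8 the rates are 15.2% and 4%. Table 3 states 84% power at 71 versus 142. A two-sided pooled normal approximation gives 78.4%:

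- pooled rate = (71 × 0.152 + 142 × 0.04)/213 = 0.0773
- standard error under the null = 0.0388; under the alternative = 0.0457
- power = Φ[(0.112 − 1.96 × 0.0388)/0.0457] = 78.4%

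The gap from 84% is a separate matter and does not bear on this point. On the same basis, with Group II kept at 142:

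- 10% set aside (64 exposed): 76.4%
- 20% set aside (57 exposed): 74.1%

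**The case against.** The strongest reply has four parts.

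- **The choice is deliberate and secondary.** Group II is meant as a teratogen-free general population comparator and is not disease-matched. Disease is fully aliased with evolocumab in this contrast, so restriction would still not isolate a drug effect. That stands as a limit on what the Group II comparison can show. It does not justify leaving in a second difference that can be removed.
- **Adjustment is planned and the data exist.** Section 9.7.2.5.2 provides for adjusted estimates and medication is recorded. A reader might infer that regression cannot help because teratogen use is absent from Group II. The documents do not support that: teratogen use can vary within the exposed cohort, and a main-effects model identifies the evolocumab effect if there is no interaction. What remains is that the protocol does not name teratogen exposure as an adjustment variable.
- **The co-medication passages are weaker than they look.** Section 9.9 speaks of LDL-lowering drugs, and nothing in the protocol calls these known teratogens. It therefore does not show that teratogen use is heavier in the exposed cohort. The Appendix B remark is a checklist comment, does not say that co-medication will only be described, and sits beside a Yes on adjusting for confounding in item 10.5. It does not rule out adjustment, although it fits poorly with Section 9.7.2.5.2.
- **The remedy is SAP detail.** A flag and a restricted set could be in a SAP that is not shown. That is fair for the wording, but the asymmetry comes from an eligibility rule that the protocol itself fixes.

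**Conclusion.** The point holds in a limited form. The one-sided teratogen exclusion biases the crude Group II comparison upward if any exposed women took a listed teratogen, unless the cohort is restricted in the same way or co-exposure is adjusted for. The protocol specifies neither for this comparison.

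The size cannot be determined from the documents. It depends on p, on r and on which drugs the OTIS Research Center counts as teratogens. Over the assumed range the null RR is 1.05 to 1.40, in a study sized for an RR of 3.8, and the bias is negligible if few women are co-exposed.

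A reader might go further and conclude that the primary result is compromised, or that an excess against Group II could never be separated from co-medication. Neither follows. The Group I comparison has no teratogen rule on either side, and restriction or a main-effects model can separate the two. This is a worthwhile, inexpensive improvement to a secondary comparison.

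**What to change.** 1. Have the OTIS Research Center apply the teratogen determination it already makes for Group II to every exposed-cohort and Group I pregnancy, as a yes/no flag assigned blind to outcome.
2. In Section 9.7.2.5.2, report the Group II comparison restricted to teratogen-free exposed pregnancies, alongside the unrestricted comparison.
3. For the Group I comparison, keep all women and add a sensitivity analysis limited to teratogen-free pregnancies in both groups.
4. Reconcile Section 9.7.2.5.2 with the Appendix B comment on whether co-medication enters the adjusted analyses.

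No new data are needed, because medication use is already collected at scheduled interviews. The work is one coded variable and some analysis wording. Eligibility and the primary analysis set do not change. The downside is a smaller exposed group in the restricted Group II comparison, with the modest power loss shown in step 5 of the working. Presenting the unrestricted result beside it keeps the full cohort visible.

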9.2.3.2 Exclusion Criteria

(1) Specific Evolocumab-Exposed Cohort

- Women who first contact the Registry after prenatal diagnosis of a major structural **birth** defect
- Women who were exposed to a different PCSK9 inhibitor during their current pregnancy or at any time within 5 half-lives prior to the first day of the LMP
- Women who have enrolled in this Registry with a previous pregnancy

(2) Comparison Group I

- Women who first contact the Registry after prenatal diagnosis of a major structural **birth** defect
- Women who have enrolled in this Registry with a previous pregnancy
- Women who were exposed to **any** PCSK9 inhibitor during their current pregnancy or at any time within 5 half-lives prior to the first day of the LMP

(3) Comparison Group II

- Women who first contact the Registry after prenatal diagnosis of a major structural **birth** defect
- Women who were exposed to any PCSK9 inhibitor during their current pregnancy or at any time within 5 half-lives prior to the first day of the LMP
- Women who have enrolled in this Registry with a previous pregnancy

(4) General Evolocumab-Exposed Case Series

- None

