- Qualified subjects will be women with exposure to evolocumab during pregnancy who do not meet the criteria for the Specific Evolocumab-Exposed cohort for reasons including (but not limited to): they do not have ASCVD, or hypercholesterolemia associated with FH (off-label use), they were exposed to evolocumab but the pregnancy has already completed, they enrolled in the cohort study with a previous pregnancy, or they already have a prenatal diagnosis of a major **structural** birth defect.

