9.7.2.6 Sensitivity Analysis

Because early prenatal diagnostic testing is prevalent in the US and increasingly performed prior to the second trimester, it is not feasible to exclude all pregnancies with prior prenatal testing from the analysis. Thus, the Registry will include pregnancies that are enrolled prior to outcome but after a prenatal test has been performed, as long as the test does not indicate a major structural **birth** defect. Because of the possibility that this practice could potentially bias the results, analyses for the primary outcome of major **structural** birth defects will be stratified by use of prenatal testing and on gestational timing of enrollment (prior to prenatal testing).

The intention of the primary endpoint is to analyze pregnancies with evolocumab exposure occurring in the first trimester. In the event that there are exposures in the second and third trimester, sub-analyses will be conducted based on length of exposure and timing of exposure, when feasible.

Outcomes that can be adjudicated as not associated with drug exposure will not be included in the primary analysis. Those outcomes, such as chromosomal and genetic abnormalities, that cannot be adjudicated as not associated with drug exposure will be analyzed in the primary analysis as well as in multiple sensitivity analyses that will be designed to address the specific outcomes observed and are impractical to fully pre-specify. However, they will be in keeping with other ongoing studies, advice received from experts, and current and evolving FDA registry guidance.

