Another limitation of the study design relates to the evaluation of spontaneous abortion rates. Rates of early spontaneous abortion (ie, at < 6-7 weeks post-LMP) will not be measured in a study that enrolls women after recognition of pregnancy. The study results with respect to spontaneous abortion will be limited to hazards of late first-trimester and early second- trimester pregnancy loss.

Because early prenatal diagnostic testing is prevalent in the US and Canada and increasingly performed prior to the second trimester, it may be difficult to achieve adequate numbers of subjects if all pregnancies with prior prenatal testing are excluded from the analysis. Therefore, the Registry will include pregnancies in the cohort study that are enrolled prior to outcome but after a prenatal test has been performed, as long as the test does not indicate a major structural **birth** defect. The FDA guidance document acknowledges that such an approach may be necessary to accrue adequate numbers ([FDA, 2002](#)). However, this practice could potentially bias the results by lowering the overall incidence of birth defects. The data analysis will address this by stratifying on use of prenatal testing and on gestational timing of enrollment (prior to prenatal testing). In addition, women who are excluded from the cohort portion of the study due to prenatal diagnosis of a major **structural birth** defect prior to enrollment will be eligible for enrollment in the Registry General Evolocumab-Exposed case series; thus these data will be captured.

It is expected that some exposures to evolocumab will occur in unintended pregnancies and unplanned pregnancy may be risk factor for adverse outcomes, for example, because the mother does not start taking prenatal vitamins until after recognition of pregnancy. Although more than half of all pregnancies in the US are unintended ([Henshaw, 1998](#)), it is possible there could be imbalances among comparison groups. This factor will be taken into consideration in the recruitment of comparison groups using the results from the interim analysis as a guide for correcting imbalances in the future. However, differences between groups will also be addressed in the statistical analysis.

The study design has relative strengths with respect to the control of a large number of potential confounders. Information will be collected repeatedly throughout pregnancy on

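### The prenatal-diagnosis exclusion has different time points in different sections, and it names fewer abnormalities than the primary analysis may count

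*Protocol*

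**What the plan says.** **Timing.** The protocol states the exclusion in five places.

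- Section 9.2.3.2, for cohorts 1 to 3: "Women who first contact the Registry after prenatal diagnosis of a major structural" birth defect. The Abstract (Section 4) uses the same trigger, first contact.
- Section 9.7.2.6 admits pregnancies "enrolled prior to outcome but after a prenatal test has been performed, as long as the test does not indicate a major structural" [defect]; its reference point is enrollment.
- Section 9.9 repeats that rule and adds that women excluded for a prenatally diagnosed "defect prior to enrollment will be eligible for enrollment in the Registry General Evolocumab-Exposed case series". The reference point is again enrollment.
- Section 9.2.3.1, item 4, lists among the reasons for entering the case series that "they already have a prenatal diagnosis of a major" structural birth defect. No time point is given.

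**Scope.** All of these name a major structural defect and nothing else. On the outcome side, Section 9.7.2.5.1 says "Outcomes that are adjudicated as not associated with drug exposure will be excluded from the primary analysis". Section 9.7.2.6 then says that outcomes "such as chromosomal and genetic abnormalities, that cannot be adjudicated as not associated with drug exposure will be analyzed in the primary analysis". Section 9.7.2.6.4 plans a sensitivity analysis without chromosomal anomalies, which makes sense only if the primary analysis can contain them.

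**The concern.** A cohort is prospective for an outcome only if women join without knowing that outcome. The exclusion protects this for the primary endpoint, so its time point and scope need to be unambiguous.

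On timing, two staff members could classify the same woman differently and each be following the protocol. On scope, the findings that bar entry are worded more narrowly than the findings that can count as cases. A woman with a known abnormal chromosomal or genetic result and no structural finding is not expressly barred anywhere, yet her pregnancy can be counted as an event.

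The stake is the primary relative risk. So few events are expected that one or two known cases can matter if they enter one cohort more readily than the other. Section 9.9 discusses the bias from enrolling after a reassuring test, which lowers observed incidence. It does not discuss enrollment after an adverse result.

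**Working it through.** **1. Can contact and enrollment be separate?** Table 1 in Section 9.1 lists contact or referral, enrollment with consent, and the intake interview as separate rows, and the text of that section describes enrollment as a voluntary, consented step after contact. Section 10.1.1 requires written parental consent before intake for women under 18. Section 9.2.2.1 says a woman can be enrolled, and her eligibility checked, on contact. A gap is therefore possible but need not occur.

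**2. A woman diagnosed with a structural defect after contact and before consent.**

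| Section | Reference point | Result |
|---|---|---|
| 4 and 9.2.3.2 | first contact | not excluded |
| 9.7.2.6 and 9.9 | enrollment | excluded |
| 9.2.3.1, item 4 (exposed women) | none | sent to the case series |

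**3. A woman with a known chromosomal or genetic result and no structural finding.** None of the five places expressly excludes her. Her pregnancy counts as a primary-outcome case if the abnormality cannot be adjudicated as unrelated to the drug.

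**4. The plan's own figures.** Section 9.5: 75 × 0.95 = 71.25 and 150 × 0.95 = 142.5, which gives the stated 71 and 142. At the 4% baseline rate the expected cases are 71 × 0.04 = 2.84 and 142 × 0.04 = 5.68. Table 3 gives 84% power at a relative risk of 3.8 (15.2% against 4%). With a two-sided 5% test I obtain 76.4% (Fisher, exact enumeration), 79.7% (chi-square, exact enumeration) and 78.4% (normal approximation). The last two are close to the 80% in the Abstract. The gap to 84% is a separate matter; I use 76.4% as the reference below.

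**5. Effect of known cases.** Let m be the number of women who enter with a known counted outcome. The documents do not give m, so 0 to 3 is an assumption. Everyone else has a 4% risk unless stated.

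- Entry into the exposed cohort only: expected rate = (m + (71 − m) × 0.04) / 71, and relative risk = that rate / 0.04. For m = 1: (1 + 2.80) / 71 = 5.35%, giving 1.34.
- Entry into Comparison Group I only: expected rate = (m + (142 − m) × 0.04) / 142, and relative risk = 0.04 / that rate. For m = 1: (1 + 5.64) / 142 = 4.68%, giving 0.86.

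| m | Exposed only: rate | Exposed only: RR (true 1.0) | Exposed only: chance of a false finding of harm (Fisher) | Comparators only: RR (true 1.0) | Comparators only: power at true RR 3.8 (Fisher) |
|---|---|---|---|---|---|
| 0 | 4.0% | 1.00 | 2.3% | 1.00 | 76.4% |
| 1 | 5.4% | 1.34 | 4.9% | 0.86 | 69.0% |
| 2 | 6.7% | 1.68 | 9.4% | 0.75 | 61.0% |
| 3 | 8.1% | 2.01 | 16.8% | 0.66 | 52.7% |

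- Balanced entry, 1 of 71 and 2 of 142: (1 + 2.80) / 71 = 5.35% and (2 + 5.60) / 142 = 5.35%, so the relative risk is 1.00.

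The direction and size depend on how unequal entry is, which the documents do not let one estimate.

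**The case against.** A reader might infer that women who already know of a structural defect have an open route into the primary analysis. The documents do not support that. Sections 9.7.2.6 and 9.9 would keep such a woman out, and Section 9.2.3.1 would send her to the case series if exposed. Section 9.2.2.1 also allows enrollment on contact, and Section 9.5 expects enrollment at 7-10 weeks on average. For structural defects this is a contradiction to reconcile and nothing more. The average does not remove it, since Table 1 provides for enrollment even after 30 weeks.

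On chromosomal findings, eligibility and outcome use the same term, and Section 9.3.2.1 defines it by a coding manual that is not in the documents. If the manual covers chromosomal anomalies, the exclusion arguably does too. Counting them is also conditional on adjudication. Both points stand as qualifications, but neither puts the exclusion into words.

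The identical criterion applies to all three cohorts, so entry could be balanced, with no bias in the relative risk. That stands too: differential motive to enroll is plausible but is not shown in the documents.

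Finally, Sections 9.7.2.6 and 9.7.2.6.2 stratify on prenatal testing, and the stratum enrolled before any test cannot contain prenatally known outcomes. This helps, as does the analysis without chromosomal anomalies. Both leave such women in the primary estimate, and stratifying spreads very few expected cases more thinly.

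**Conclusion.** The concern holds in a limited form. The time point is inconsistent: first contact in Sections 4 and 9.2.3.2, enrollment in Sections 9.7.2.6 and 9.9, and none in Section 9.2.3.1. Separately, and more importantly, the exclusion names only structural defects, while the primary analysis can count chromosomal and genetic abnormalities. Unless the coding manual closes that gap, a woman who knows such a result may enroll and count as a case.

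The size is illustrative. One or two known cases in the exposed cohort alone would move a null relative risk to about 1.34 or 1.68, the same numbers among comparators alone would move it to about 0.86 or 0.75, and balanced entry would leave it at 1.0. These figures rest on a 4% baseline, 71 and 142 pregnancies, and an assumed number of entrants. A reader might take 1.34 to 1.68 as the bias to be expected; the documents give no count of entrants and no evidence of unequal entry, so they do not support that.

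**What to change.** - Use one time point, a diagnosis made before enrollment and consent, for cohorts 1 to 3 in Sections 4, 9.2.3.2, 9.7.2.6 and 9.9, and in the case-series item of Section 9.2.3.1.
- Extend the exclusion to any prenatally known abnormality that would count toward the primary outcome, and say explicitly whether this covers chromosomal and genetic findings.
- Route exposed women excluded on this ground to the General Evolocumab-Exposed Case Series. The list of reasons in Section 9.2.3.1 is already open-ended.
- Tabulate these exclusions by cohort, so that unequal entry or exclusion can be seen.

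The cost is mainly protocol wording. A few pregnancies would leave the cohorts; the exposed ones would still be followed. A question on prenatal test results may have to be added at the eligibility check or intake, because the intake topics in Section 9.2.5 do not list them; Sections 9.4.2 and 9.4.3 collect them at the interim and outcome interviews.
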